### **6.3. Validity and reliability of data**

The research methodology for this project is based on methodologies used in similar studies. To improve the validity of results, potential confounding variables will be statistically adjusted for in the analysis, and inpatients receiving transfusions other than red blood cells will be excluded.

This study will investigate consecutive adult surgical admissions to three public hospitals for specialties where blood is commonly transfused. Given the study design and the broad inclusion criteria applied, the results are expected to have external validity and are likely generalizable to other surgical inpatients admitted to large teaching hospitals internationally.

Exposure and outcome variables have been carefully selected and are known to be accurately measured. Results from laboratory testing will be used to measure nadir haemoglobin values to accurately define the degree of anaemia. The cut-offs for haemoglobin levels have been selected based on other studies.

The in-hospital and 30-day mortality outcome measures selected for this study are well-defined objective measures and will be coded as binary variables (yes/no). Hospital length of stay, also a frequently studied objective outcome measure will be calculated in days from admission to discharge. All outcomes variables will be measured in the same way between the different subgroups.

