## **6. Research Plan**

### **6.1. Description of population and sample.**

This project will include all adults admitted as elective or emergency cases for selected surgical specialties to three hospitals in Western Australia between July 2008 and June 2017. Local studies show that the following six specialties account for the majority of blood transfused in surgical patients.

- Orthopaedics
- Gastrointestinal Surgery
- Vascular Surgery
- Urology
- Cardiothoracic surgery
- Neurosurgery

Any patients transfused fresh frozen plasma, platelets, and cryoprecipitate will be excluded from the study. This is to reduce the possibility of confounding as the purpose of this study is to focus on nadir haemoglobin levels, red blood cell transfusion and their effect of mortality and length of stay.

Also excluded are patients receiving a massive transfusion (defined as 5 units of red blood cells in 4 hours or 10 units in 24 hours), patients transfused any blood products 90 days prior to admission, patients with a length of stay of less than 2 days (same day and overnight admissions), patients under the age of 18 years at admission, and patients with no haemoglobin results.

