## **6.2. Description of data gathering methods, including definitions of variables.**

The majority of data needed for this project will be sourced from the *Western Australian Patient Blood Management System*. The advantages of sourcing the majority of data from one system include consistent data collection processes and classification of variables.

The exposure variables of interest are degree of anaemia and red blood cell transfusion. Anaemia will be defined using the nadir haemoglobin result during admission for those not transfused and the pre-transfusion haemoglobin result in patients transfused, as described previously. The pre-transfusion haemoglobin will be the closest level measured prior to the first red blood cell transfusion administered. Fridges are available for storing blood in theatres and because of this the timing of red blood cell transfusion in the operating room is unknown. Therefore for patients transfused in the operating room the nadir haemoglobin result will be used as a surrogate for the pre-transfusion haemoglobin result. Haemoglobin levels will be grouped into the following categories: below 50 g/L, 50-59 g/L, 60-69 g/L, 70-79 g/L, 80-89 g/L, 90-99 g/L, 100 g/L or over. These cutoffs were selected after reviewing similar studies.

The main outcome variables of interest are mortality and hospital length of stay of current admission. For the mortality analysis, both in-hospital and 30-day all-cause mortality will be assessed. In-hospital and 30-day mortality will be calculated from date of death recorded in hospital patient admission systems (TOPAS/WebPas). Potential confounders collected will include age at admission, sex, hospital, discharge year, admission type (emergency or elective), clinical specialty, and patient comorbidities.

Patient comorbidities will be assigned a score based on the Charlson Comorbidity Index derived from ICD-10 codes for the comorbidities identified. To ensure the Charlson score represents patient comorbidities on admission, hospital-acquired complications will be excluded from the calculation.

Other data items to be collected include admission date, discharge date, discharge specialty, diagnosis related group, hours in ICU, presence of a red blood cell transfusion (yes/no), had a massive transfusion (yes/no), and number of red blood cell units transfused.

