### **6.4. Statistical methods.**

Exposure and outcome variables will initially be described by univariate and bivariate statistics, the latter using the chi-squared test for categorical variables and independent samples t-test for continuous variables. Logistic regression models will be applied to test the relationship that both red blood cell transfusion and nadir haemoglobin levels have with in-hospital mortality and 30-day mortality. A zero-truncated negative binomial regression model will be applied to the length of stay outcome. All regression models will adjust for the same potential confounders. A robust variance adjustment will be applied to the regression models to account for any potential correlation between multiple admissions for the same patient.

For this analysis we are also interested in whether the presence of a red blood cell transfusion modifies the effect of nadir haemoglobin on in-hospital mortality, 30-day mortality and length of stay. To test any effect modification on outcome an interaction term between nadir haemoglobin level and red blood cell transfusion will be added to the multivariable logistic regression models. Only significant interactions (defined as p-values <0.05) will be reported, with calculated odds ratios for interaction terms presented.

In addition, Kaplan-Meier curves and Cox proportional hazards models will be plotted to show time to death in patients transfused red blood cells when compared to patients not transfused red blood cells across the various nadir haemoglobin levels.

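### Length of stay is counted from admission, but transfusion and nadir haemoglobin arise during that same stay, so the planned stay model is biased towards longer stays with transfusion even under no effect

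*Protocol*

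**What the plan says.** - **Outcome.** Protocol 6.3: "Hospital length of stay, also a frequently studied objective outcome measure will be calculated in days from admission to discharge".
- **Transfusion.** Protocol 6.2 lists it as one indicator per admission: "presence of a red blood cell transfusion (yes/no").
- **Haemoglobin.** Protocol 6.2: "Anaemia will be defined using the nadir haemoglobin result during admission for those not transfused and the pre-transfusion haemoglobin result in patients transfused". For transfused patients, "The pre-transfusion haemoglobin will be the closest level measured prior to the first red blood cell transfusion administered". Theatre timing is unknown, so "for patients transfused in the operating room the nadir haemoglobin result will be used as a surrogate for the pre-transfusion haemoglobin result".
- **Model.** Protocol 6.4: "A zero-truncated negative binomial regression model will be applied to the length of stay outcome". The confounders in 6.2 are age, sex, hospital, discharge year, admission type, specialty and comorbidity. None carries the time of exposure.
- **Population.** Section 6.1 excludes stays shorter than 2 days, so every patient reaches day 2.

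No section sets a landmark, limits the exposure window or updates exposure over time. The Kaplan-Meier and Cox analyses in 6.4 concern death, not discharge.

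**The concern.** The interval in which a patient can become exposed is the interval whose length is the outcome. Someone first transfused on day 12 had to remain in hospital until day 12 to be classed as transfused, and that time is then counted as part of the outcome attributed to transfusion. A patient who goes home on day 3 had little chance to be transfused and few haemoglobin draws from which a low minimum could arise.

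This is not ordinary confounding. It appears even if transfusion is independent of prognosis, so better baseline covariates do not remove it.

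Length of stay is a main outcome and appears in both objectives in section 3. With the 60,000 to 70,000 admissions expected in 6.5, a ratio produced by the counting rule alone would be estimated precisely and could be read as a finding.

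**Working it through.** The protocol gives no mean stay, effect size or transfusion timing, so there is no stated figure to reproduce. The check asks what the planned comparison returns when transfusion and haemoglobin have no effect on stay (true ratio 1.00).

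**Inputs from the protocol:** stay of at least 2 days (6.1); exposure rule and seven haemoglobin bands (6.2); zero-truncated negative binomial model (6.4); 65,000 admissions, within the range in 6.5.

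**Assumptions, not in the protocol:** stay = 2 + a negative binomial count with mean 5 and size 1.2, and the transfusion timings stated below.

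**Step 1, mechanism.** With a daily transfusion chance h, P(transfused | stay L) = 1 − (1 − h)^L. With h = 0.02:
- L = 3: 1 − 0.98³ = 5.9%.
- L = 25: 1 − 0.98²⁵ = 39.7%.

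**Step 2, crude ratio with transfusions spread evenly.** For small h the chance is roughly proportional to L. The mean stay of the transfused is then about E(L²)/E(L) = μ(1 + CV²), that of the others about μ, and the ratio about 1 + CV².
- Here μ = 2 + 5 = 7, variance = 5 + 5²/1.2 = 25.83, CV² = 25.83/49 = 0.527, ratio ≈ 1.53.
- Simulation agrees: at h = 0.01, mean stays of 10.47 and 6.74 days give 1.55. Over h = 0.5% to 5% the crude ratio was 1.54 to 1.64, and the zero-truncated model gave 1.58 to 1.68.

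**Step 3, the protocol's haemoglobin rule.** Daily haemoglobin was allowed to drift (starting mean 108 g/L, SD 15). The transfusion chance rose as current haemoglobin fell. Exposure was the nadir if not transfused and the pre-transfusion level if transfused; the theatre surrogate was not simulated. Between 2.0% and 3.3% were transfused, at a median of day 4 to 5.

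| Setting | Crude | Adjusted for band | 60-69 g/L | 70-79 g/L | 80-89 g/L |
|---|---|---|---|---|---|
| Haemoglobin measured daily | 1.51 | 1.33 | 1.31 | 1.30 | 1.34 |
| Measured on 40% of days after day 1 | 1.52 | 1.27 | 1.21 | 1.26 | 1.27 |
| Daily, day-1 transfusion chance cut to one fifth | 1.56 | 1.40 | 1.40 | 1.37 | 1.37 |

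Below 60 g/L the cells were too small to read. Among the non-transfused, mean stay was 6.5 days at 100 g/L or over and 8.3 to 8.6 days at 70-79 g/L, although haemoglobin had no effect on stay.

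**Step 4, sensitivity to timing (crude ratio).**

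| Share of transfusions on day 1 | 16% | 36% | 57% | 78% | 91% | 100% |
|---|---|---|---|---|---|---|
| Ratio | 1.56 | 1.44 | 1.30 | 1.15 | 1.06 | 0.98 |

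**Step 5, time-aligned comparison.** For the Step 4 data, the remaining stay of patients transfused on day d was compared with that of patients still in hospital and not yet transfused on day d. The ratio was 0.98 to 1.01 throughout. In separate simulations with log-normal stays, a day-2 landmark comparison of remaining days gave 0.99 to 1.01.

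**The case against.** **Surgical transfusions may cluster early.** Section 6.2 expressly foresees transfusion in theatre. A null simulation with only about 9% to 10% of transfusions after day 2 gave crude ratios of 1.05 to 1.11; with all of them on days 0 to 2 it gave 1.00. This stands as a limit on size. It does not remove the bias, because the pre-transfusion rule in 6.2 applies to a first transfusion on any day and the protocol does not say when transfusions occur.

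**A reader might infer that the planned analysis would show stays 1.6 to 2.2 times as long.** Crude ratios of that size do arise with an even daily transfusion chance and widely spread stays, but the planned analysis also involves haemoglobin level. Within a low band, non-transfused patients were themselves selected for long stays by their whole-stay nadir. That lengthens the comparator's stay, so the two artefacts partly offset each other. Step 3 shows the drop from 1.51-1.56 to 1.27-1.40.

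**A reader might infer that every patient's haemoglobin is a whole-stay minimum.** That is so only for non-transfused and theatre-transfused patients. For the others, draws after the first transfusion do not count.

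**A reader might infer that the plan will report a false interaction on stay.** Section 6.4 states an interest in effect modification of length of stay but adds the interaction term only to the logistic models. The bias can differ between bands and could imitate effect modification if an interaction is fitted to stay. The protocol does not clearly say that one will be.

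**Only association is claimed.** Section 3 is worded that way, but 6.1 describes the purpose as an effect on mortality and length of stay. An association created by the counting rule tells the reader little in either case.

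**Conclusion.** The point holds. As fixed in 6.2 to 6.4, the length-of-stay model favours longer stays with transfusion when there is no effect, and adjustment for haemoglobin band reduces this without removing it. The direction follows from the definitions unless practically all transfusions occur at admission.

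The size is not known from the protocol. About 1.3 to 1.4 after haemoglobin adjustment applies to transfusions spread over the stay, under the assumed stay distribution and haemoglobin process. The fall towards 1.0 with early transfusion was computed for the crude ratio only. The real figure depends on the timing and spread of stay in the data.

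The point is confined to length of stay. The documents give no ground for extending it to the in-hospital or 30-day mortality analyses.

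**What to change.** Amend 6.2 to 6.4 before analysis.

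- **Main length-of-stay analysis, preferred:** a daily time-to-discharge model in which transfusion status and lowest haemoglobin so far are updated each day, with in-hospital death as a competing event.
- **Alternative:** a day-2 landmark. Classify transfusion and lowest haemoglobin by day 2, then model the remaining days, with in-hospital death handled explicitly. Stays of exactly 2 days then have zero days left: 7% to 12% of stays under the assumed log-normal distributions, and (1.2/6.2)^1.2 = 14% under the distribution in Step 2. The zero-truncated model must be replaced by one that allows zeros.
- **Data:** add the operation date, which is not among the items listed in 6.2, as the proxy for theatre transfusion timing. Ward transfusions and haemoglobin results must already be timed to apply the pre-transfusion rule.
- **Existing comparison:** keep the admission-to-discharge contrast of ever against never transfused as descriptive only, with the bias stated.
- **Effect modification:** if an interaction is to be tested for stay, say so and fit it in the time-aligned model.

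**Cost:** one added data item and more programming. In the landmark version, later transfusions count as not yet exposed (0% to 73% of all transfusions across the simulated timings). This dilutes the contrast, could thin the low haemoglobin bands, and answers a narrower question than objective 1. The daily model avoids that loss.

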### **6.4. Statistical methods.**

Exposure and outcome variables will initially be described by univariate and bivariate statistics, the latter using the chi-squared test for categorical variables and independent samples t-test for continuous variables. Logistic regression models will be applied to test the relationship that both red blood cell transfusion and nadir haemoglobin levels have with in-hospital mortality and 30-day mortality. A zero-truncated negative binomial regression model will be applied to the length of stay outcome. All regression models will adjust for the same potential confounders. A robust variance adjustment will be applied to the regression models to account for any potential correlation between multiple admissions for the same patient.

For this analysis we are also interested in whether the presence of a red blood cell transfusion modifies the effect of nadir haemoglobin on in-hospital mortality, 30-day mortality and length of stay. To test any effect modification on outcome an interaction term between nadir haemoglobin level and red blood cell transfusion will be added to the multivariable logistic regression models. Only significant interactions (defined as p-values <0.05) will be reported, with calculated odds ratios for interaction terms presented.

In addition, Kaplan-Meier curves and Cox proportional hazards models will be plotted to show time to death in patients transfused red blood cells when compared to patients not transfused red blood cells across the various nadir haemoglobin levels.

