## 6.5. Sample size estimation.

Given the inclusion and exclusion criteria, there are expected to be between 60,000-70,000 consecutive inpatient admissions in the study cohort.

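### The length-of-stay model is truncated at zero although the cohort contains no stay under 2 days, so the stated likelihood has the wrong truncation point

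*Protocol*

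**What the plan says.** Three statements in the protocol bear on this.

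- Section 6.1 lists among the exclusions "patients with a length of stay of less than 2 days (same day and overnight admissions".
- Section 6.3 defines the outcome: "Hospital length of stay, also a frequently studied objective outcome measure will be calculated in days from admission to discharge". It subtracts nothing from the count.
- Section 6.4 fixes the model: "A zero-truncated negative binomial regression model will be applied to the length of stay outcome".

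Section 6.4 also says "All regression models will adjust for the same potential confounders", and adds: "A robust variance adjustment will be applied to the regression models to account for any potential correlation between multiple admissions for the same patient". It lists as a question of interest "whether the presence of a red blood cell transfusion modifies the effect of nadir haemoglobin on in-hospital mortality, 30-day mortality and length of stay". Section 6.5 gives the expected size: "there are expected to be between 60,000-70,000 consecutive inpatient admissions in the study cohort". No section gives a mean, dispersion or expected ratio for length of stay.

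**The concern.** A truncated count model must be truncated where the data are. With values 0 and 1 both removed by design, the support is 2, 3, and so on. The zero-truncated likelihood conditions on 1 or more. To accommodate the absence of 1-day stays, the fit has to distort its mean and dispersion parameters.

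Length of stay is one of the three outcomes in both objectives (section 3). The robust variance changes standard errors, not coefficients. With 60,000 or more admissions, intervals could be narrow around a shifted value. The protocol itself names the model, so this is not a detail left open for a later analysis plan.

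**Working it through.** **Support.** Same-day is 0 days and overnight is 1 day. Both are excluded, so the minimum is 2. The zero-truncated model gives positive probability to 1. The two sections agree only if the outcome is shifted, and no shift is stated.

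**Size.** The protocol has no length-of-stay figure to reproduce. Everything below is assumed: negative binomial stays with variance μ + aμ², the same dispersion a in both groups, 15% exposed, stays kept only if 2 or more. Large-sample estimates come from maximising the expected log-likelihood of each model.

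Formulas: P(0) = (1 + aμ)^(−1/a); P(1) = μ(1 + aμ)^(−1/a − 1); cohort mean = (μ − P(1)) / (1 − P(0) − P(1)).

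**Worked case: reference mean 4, a = 1.0, true ratio 1.50.**

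- Reference: P(0) = 1/5 = 0.200; P(1) = 4/25 = 0.160; kept 0.640; cohort mean = (4 − 0.160)/0.640 = 6.00.
- Exposed (mean 6): P(0) = 1/7 = 0.143; P(1) = 6/49 = 0.122; kept 0.735; cohort mean = (6 − 0.122)/0.735 = 8.00.
- Ratio of cohort means: 8.00/6.00 = 1.333.
- Zero-truncated fit: ratio 1.364, dispersion 0.39 instead of 1.0, and 9% of reference-group stays predicted at 1 day.
- Share of log ratio lost: 1 − ln(1.364)/ln(1.50) = 23%.
- Fit conditioned on 2 or more: ratio 1.500.

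**Range for a true ratio of 1.50.** The mean is the untruncated reference mean.

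| Mean | a | P(0)+P(1), reference | Zero-truncated ratio | Fitted a | Ratio of cohort means |
|---|---|---|---|---|---|
| 3 | 0.7 | 0.39 | 1.33 | 0.21 | 1.30 |
| 4 | 1.0 | 0.36 | 1.36 | 0.39 | 1.33 |
| 5 | 0.7 | 0.25 | 1.39 | 0.35 | 1.37 |
| 8 | 0.7 | 0.15 | 1.44 | 0.47 | 1.42 |
| 12 | 0.7 | 0.09 | 1.46 | 0.54 | 1.45 |
| 12 | 0.3 | 0.02 | 1.48 | 0.27 | 1.48 |

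Conditioning on 2 or more returned 1.500 in every row. The predicted share at 1 day in the reference group ran from about 1% (last row) to about 11% (mean 3).

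Over 48 settings (means 3-12, dispersion 0.3-1.2, true ratios 0.8-2.0) every single-exposure ratio moved towards 1. The loss on the log scale ran from about 2% (mean 12, a = 0.3: 2.0 becomes 1.97) to about 39% (mean 3, a = 0.3: 0.80 becomes 0.87).

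**Where the pattern fails.**

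- A true ratio of 1.0, adjusted for a correlated covariate with ratio 2.0, stayed at 1.000.
- With no true interaction, the zero-truncated fit gave interaction ratios of about 1.02-1.05, or 0.98 when one main ratio was 0.8. Conditioning on 2 or more gave 1.000.
- With unequal dispersion (0.3 reference, 1.2 exposed; mean 5), a true 1.5 became 1.78 zero-truncated and 1.98 conditioned on 2 or more. A true 1.0 became 1.30 and 1.38.
- With discretised lognormal stays, a true 1.5 became 1.44-1.49 zero-truncated and 1.59-1.64 conditioned on 2 or more.

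**The case against.** The strongest reply is that attenuation is measured against a parameter that the protocol never names as its target. The ratio of 1.50 describes an untruncated population that includes the same-day and overnight stays that the study removes. Against the ratio of mean stays in the analysed cohort, the zero-truncated coefficient is close and slightly above (1.364 against 1.333 in the worked case). The same fit reproduces the cohort mean stays of 6.00 and 8.00. A reader might infer that predicted mean stays are wrong; in this two-group model they are not. What is wrong is the dispersion and the probability placed at 1 day.

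The reply continues that the loss is near zero if stays are long, that no stay distribution is given, and that the matching truncation is not better under every distribution, as the lognormal and unequal-dispersion runs show.

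All of this stands, and it limits what can be said about size and direction. It does not remove the mismatch between sections 6.1 and 6.4: no choice of target makes a 1-day stay possible in this cohort. It also shows a related gap, since the protocol does not say which ratio it means to report.

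**Conclusion.** The truncation point in section 6.4 is inconsistent with the exclusion in section 6.1, and this follows from the text alone. The consequences are conditional. With negative binomial stays of common dispersion, the planned model underestimates dispersion and generally attenuates non-null main-effect ratios on the untruncated scale, by an amount governed by the share of latent stays below 2 days. For a true 1.50 the estimate runs from about 1.33 to 1.48 for assumed means of 3 to 12 days; across all settings the loss is roughly 2-39% of the log ratio. Interaction ratios can move slightly away from 1, which would matter if an interaction is fitted for length of stay.

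A reader might infer that every length-of-stay ratio shrinks. The document does not support that: null ratios need not move, direction can reverse under unequal dispersion, and no mean or dispersion is given from which to fix a magnitude. The mortality models are unaffected. The specification should be corrected, but a material bias in this study has not been shown.

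**What to change.** In section 6.4, replace the zero-truncated model with a negative binomial model left-truncated at 1, that is, conditioned on stays of 2 days or more. Alternatively, state a shifted outcome, such as stay minus 2 with an untruncated model, and note that its ratio then refers to the shifted days.

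Add one sentence saying whether the reported ratio refers to the untruncated mean or to mean stay in the analysed cohort. Add a check of fitted against observed counts at 2, 3 and 4 days.

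The cost is a few sentences and slightly more analysis work; no new data are needed, and cohort and objectives are unchanged. The correctly truncated model remains sensitive to the negative binomial assumption, and the check at low counts is there to reveal a poor fit.

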### **3. Objectives**

The specific objectives addressed by the study are:

1. Is there an association between in-hospital mortality, 30-day mortality, and hospital length of stay and red blood cell transfusion at various levels of nadir haemoglobin?
2. Is there an effect modification between levels of nadir haemoglobin and presence of a red blood cell transfusion on in-hospital mortality, 30-day mortality, and length of stay?

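### The effect-modification model names only the haemoglobin x transfusion product, so a confounder tied to transfusion whose effect on death varies by haemoglobin can bias that interaction

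*Protocol*

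**What the plan says.** Protocol section 6.4 plans logistic models for in-hospital and 30-day mortality. On adjustment it states: "All regression models will adjust for the same potential confounders". Section 6.2 lists these as "age at admission, sex, hospital, discharge year, admission type (emergency or elective), clinical specialty, and patient comorbidities", with comorbidity summarised by a Charlson score.

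For effect modification, section 6.4 states that "an interaction term between nadir haemoglobin level and red blood cell transfusion will be added to the multivariable logistic regression models". Haemoglobin is grouped in section 6.2 as "below 50 g/L, 50-59 g/L, 60-69 g/L, 70-79 g/L, 80-89 g/L, 90-99 g/L, 100 g/L or over". The reporting rule follows: "Only significant interactions (defined as p-values <0.05) will be reported, with calculated odds ratios for interaction terms presented".

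No confounder x haemoglobin product is named. Nor does the protocol say that confounders enter as main effects only, or that haemoglobin-stratified adjustment is excluded.

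**The concern.** A confounder entered as a single term is assumed to have the same log odds ratio for death at every haemoglobin level. That usually suffices to adjust an overall transfusion effect. It does not suffice for the transfusion x haemoglobin term. If the confounder's effect changes with haemoglobin and transfused patients differ on that confounder within a level, the unmodelled change has to go somewhere, and transfusion x haemoglobin is the only product available to take it.

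The cohort makes this worth guarding against. Section 6.1 pools elective and emergency admissions from six specialties, from cardiothoracic surgery to urology. Admission type and specialty could plausibly predict transfusion at a given haemoglobin and also have a risk gradient that differs by haemoglobin.

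At stake is Objective 2, one of the two objectives. A spurious gradient could look like transfusion doing harm at high haemoglobin and good at low haemoglobin, or the reverse. Section 4 hopes that the results will inform the choice of thresholds in future trials. The bias does not shrink as the cohort grows, and publishing only interactions below p = 0.05 favours results of this kind.

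**Working it through.** **There is no figure to reproduce.** Section 6.5 says only that "there are expected to be between 60,000-70,000 consecutive inpatient admissions in the study cohort". The protocol gives no death rate, transfusion rate, effect size or power. Everything below except the seven bands, the single named product, the 0.05 level and the cohort size is assumed.

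**Step 1: the mechanism.** Let C be a binary confounder with log odds ratio g(h) for death at level h, and let g* be the single value fitted when C has no haemoglobin product. For a rare outcome and modest effects, to first order:

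fitted log OR of transfusion at h ≈ true log OR + [g(h) − g*] × [P(C=1 | transfused, h) − P(C=1 | not transfused, h)].

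The extra term is zero if g(h) is constant, or if C is unrelated to transfusion within h.

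**Step 2: rough size by hand.** Suppose 40% of non-transfused patients have C = 1 at every level, the C-transfusion odds ratio is 3, and C's odds ratio for death is 4 times larger at the highest level than at the lowest.
- Odds of C if transfused: (0.4/0.6) × 3 = 2, so the proportion is 0.667 and the difference is 0.267.
- Spurious ratio of transfusion odds ratios, lowest v highest level: exp(−ln 4 × 0.267) = exp(−0.370) = 0.69.
- Replacing 40% by 20% or 50% gives 0.73 or 0.71.

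**Step 3: fitted models.** The model with C as a main effect, and the same model plus C x haemoglobin, were fitted to expected cell counts. Settings: N = 65,000; seven levels; transfusion odds ratio 1.3 at every level, so the true interaction is zero; overall odds ratio of C for death 2; about 1,560 deaths when that odds ratio is constant. The haemoglobin distribution and the death and transfusion rates by level were also assumed. The rejection rate is P[χ²(df, λ) > χ²(df, 0.95)], where λ is the drop in deviance on adding transfusion x haemoglobin. Here df = (7−1) × (2−1) = 6 for bands, or 1 for a trend.

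| C-transfusion OR | Change in C's OR across levels | Spurious ratio, below 50 v 100 g/L or over | Rejection, 6 df | Rejection, trend |
|---|---|---|---|---|
| 1 | 8-fold | 1.00 | 0.050 | 0.050 |
| 3 | none | 1.00 | 0.050 | 0.050 |
| 2 | 2-fold | 0.90 | 0.053 | 0.058 |
| 3 | 2-fold | 0.85 | 0.058 | 0.072 |
| 2 | 4-fold | 0.81 | 0.062 | 0.085 |
| 3 | 4-fold | 0.71 | 0.083 | 0.141 |
| 3 | 8-fold | 0.60 | 0.128 | 0.251 |
| 5 | 8-fold | 0.49 | 0.245 | 0.473 |

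The 0.71 agrees with the hand value. With C x haemoglobin added, every ratio returns to 1.00 and every rate to 0.05. In simulations of 1,000 datasets each, the 6-df rate after the fix was 0.052 to 0.061; the Monte Carlo SE is √(0.05 × 0.95/1,000) = 0.007.

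**Step 4: other assumed values.** Similar fits with no transfusion effect gave trend rejection of 5.6% (2-fold, OR 2), 10.4% (4-fold, OR 3) and 15.6% (8-fold, OR 3). A separate simulation used admission type as C, about 800 deaths and no transfusion effect:
- Risk was 1.5% (emergency) v 0.15% (elective) at 100 g/L and over, an odds ratio of 10.1, and 4.7% v 3.6% at 60-69 g/L, an odds ratio of 1.3. The change is 10.14/1.32 = 7.7-fold.
- Transfusion was 20% v 6% at 80-89 g/L (odds ratio 3.9) and 50% v 25% at 70-79 g/L (odds ratio 3.0).
- False transfusion odds ratios ran from 1.14 at the top to 0.83 at 60-69 g/L. Rejection was 10.2% (trend) and 8.8% (joint), falling to 4.6% and 5.7% with the added term.
- With milder convergence the odds ratios ran from 1.06 to 0.93 and rejection was about 6%.

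The bias does not depend on the number of deaths, but the rejection rate does. That is one reason why the rates differ between settings.

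**The case against.** The strongest reply is that the protocol is silent here rather than wrong. The form of covariate adjustment is often left to a statistical analysis plan, and one may exist. A reader might infer that main-effects-only adjustment has been specified; it has not, and that reading remains an inference. What survives is that section 6.4 does choose the model for Objective 2, names its one product term, and ties reporting to that term's p-value. Improving that model is a fair comment on what is written.

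A reader might also infer that such a confounder will be reported as effect modification. The documents do not support that. The confounder must also be associated with transfusion within haemoglobin levels, and its effect must vary across them. Whether either holds in this cohort cannot be read from the protocol, and several confounders could reinforce or offset one another. The 7.7-fold admission-type scenario is near the extreme of what was examined. In its milder version, a rate of about 6% with a Monte Carlo SE of about 0.5 points (2,000 datasets) cannot be told apart from the 5.7% seen after the fix.

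It is tempting to extend the point to the haemoglobin-specific transfusion estimates for Objective 1. Section 6.4 does not say that they come from the interaction model, and fits stratified by haemoglobin would let confounder effects vary. That extension is not supported.

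Finally, an unchanged SD of 0.102 for the interaction coefficient was shown only for an added admission-type term, so it cannot by itself show that the full remedy is free. Fits with full specialty x band terms put the rise in the interaction's standard error at no more than about 1.5%.

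**Conclusion.** The point holds as a conditional, low-cost improvement. As written, the effect-modification model does not guard against a confounder that is linked to transfusion within haemoglobin levels and has a haemoglobin-dependent effect on death. Such a confounder can bias the interaction in either direction.

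The size cannot be fixed from the documents. For a trend test under assumed values, the false-positive rate is about 5-6% for mild heterogeneity, 7-14% for moderate, and 15% or more for strong, reaching 47% in the most extreme case tried. The 6-df test over bands is less affected: 5.3% to 8.3% across the mild and moderate rows of the table. With fewer deaths the rates are lower: the strong admission-type scenario with about 800 deaths gave 10.2%. There is no bias if the confounder's effect is constant across haemoglobin levels, or if it is unrelated to transfusion within them.

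**What to change.** Add a sentence to section 6.4: the models that test transfusion x haemoglobin will also include haemoglobin x admission type and haemoglobin x specialty, with haemoglobin as a score where specialty-band cells are sparse, and linear-by-linear haemoglobin x age and haemoglobin x Charlson terms; the interaction will be reported from that model. If the statistical analysis plan already contains such terms or stratified adjustment, a cross-reference is enough.

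All the variables are already collected. In bands, haemoglobin x specialty costs 5 × 6 = 30 parameters and haemoglobin x admission type 6; with a haemoglobin score they cost 5 and 1. Age and Charlson add one each. Cells below 60 g/L may be sparse if bands are used throughout, which is the reason for allowing the score. The loss of precision on the interaction is very small.
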